9.1 Handling and storage of data

The following are requirements with regards to handling and storage of data, please mark all that apply:

- | | |
|---|-------------------------------------|
| • Digital data will be archived following a strict security and back-up policy (akin to UMCG security level). |  |
| • Paper source data and study files will be archived according the UMCG policy |  |

 Source data, study files and digital data will be archived 15 years after the study is completed. 					

 Tooling (eg. software and procedures) used for collecting, processing, analysing, and storing data will be compliant with the UMCG policy and Standard Operating Procedures in the UMCG Research Toolbox. 					

9.1.1 If applicable: Not all items in the above section 10.1 apply to my study. Please elaborate on the reason for this and the solutions. NA
					

9.2 Anonymization and pseudonymization
					
Data will be anonymized during data collection.	
 
 Yes	No	
 
 		
 
	Yes	No		
Yes	No				
					

If data is anonymized:
 
 Please explain what procedure is used: NA Please reflect on the applicability of K1-anonymity on your dataset: NA 
If anonymized data please skip the rest of section 9.
					
Data will be pseudonymized during data collection (i.e. data cannot directly be linked back to the participant).	
 
 Yes	No	
 
 		
 
	Yes	No		
Yes	No				
					

If data is pseudonymized, please explain what procedure is used. During data collection direct identifiers are temporarily accessible to the study coordinator to complete essential outcome data (e.g. BIG registration). Once all required data are collected, direct identifiers (e.g. names, contact details) are replaced with a unique study code and the code list linking identifiers to pseudonyms is stored separately and securely. From that point onward only pseudonymized data are used for analysis with access restricted to the Principal Investigator and authorized study delegates.
					

9.3 Pseudonymization requirements
					

9.3.1 The following are requirements when pseudonymized data is used, please mark all that apply:
					

 Indirect and direct identifiable information collected will be minimized and only collected for the purpose of this study 					

 Direct identifiable information (e.g. contact details, code list, encryption key, participant identification log) will be stored separately from pseudonymized data 					

 Direct identifiable information can only be accessed by the Principal Investigator and study delegates after authorization by the Principal Investigator. 					

 Pseudonymized data can only be accessed by the Principal Investigator and study delegates after authorization by the Principal Investigator. 					

 Data roles, responsibilities, access and authorization, during the study and after study completion, will be managed and documented (e.g. in the DMP or study delegation log). 	

9.3.2 If applicable: not all items in the above list of pseudonymization requirements apply to my study. Please elaborate on the reason for this and the alternative solutions.
 
All pseudonymization requirements apply to this study. The only clarification is that during the data collection phase direct identifiers and research data are temporarily handled together by the study coordinator to complete essential outcome information. Once these data are recorded direct identifiers are removed and replaced by a study code with the code list stored separately and securely. From that point onward, all requirements are fully met: direct identifiers are stored separately, pseudonymized data are used for analysis only and access is restricted to the Principal Investigator and authorized study delegates. Data roles and responsibilities are documented in the delegation log
	

10. FAIR Data and Data Sharing

10.1 FAIR data The following statements concern FAIR data, which is the UMCG policy. Please note that FAIR is not the same as Open Access.			
Data will be made findable by including the description of the study (and type of data (i.e. metadata) in the UMCG FAIR data catalogue and other discipline specific catalogue(s).	Yes 	No 	
If 'no' is answered on the above question , please elaborate on the reason for this. NA			
10.2 Data Sharing			
In case data (and biomaterials) will leave or enter the UMCG, will you contact the Loket Contract Research to arrange the proper contracts? ([contact])	Yes 	No 	No data will leave or enter UMCG 

11. Management of Biomaterials (either newly collected or from an existing biobank)

11.1 Will biomaterials be collected, processed, analyzed and/or stored for the purpose of this study?	Yes 	No  skip and delete rest of section 11
11.2 Will the biomaterials be collected, specifically for this study, in a prospective manner?	Yes 	No  skip section 11.3 until 11.6. Continue with section 11.6
11.3 What biomaterials will be collected: NA		

11.4 How will the biomaterials be collected and processed: NA	
11.5 Where and how will the biomaterials be stored: NA	
11.6 What will be done with the remaining biomaterials after study completion (eg. destroyed, returned to biobank/previous study, stored) NA	
11.7 Biomaterials check-list	
11.7.1 The following are requirements for the use of biomaterials, please mark all that apply:	
• Only biomaterials required to answer the research question(s) will be collected (dataminimalisation)	
• The biomaterials will be anonymized or pseudonymized according to laws, guidelines and (if applicable) SOPs	
• Biomaterials can only be accessed by the Principal Investigator and study delegates, after authorization by the Principal Investigator	
• Biomaterials will be stored 15 years after the study is completed	
11.7.2 Not all items in the above section apply to my study. Please elaborate on the reason for this and the alternative solutions. NA	

12. Burden, Risks & Benefits

12.1 Burden Is there a (potential) burden for the participant as a result of participating in this study? For example: feeling tired after performing tests, reliving bad memories.	Yes, minimal burden 	Yes, more than minimal burden 	No 

If yes, please explain what the burden is/might be
 
The potential burden for participants is minimal. Participation involves completing a short questionnaire of approximately 10 minutes aimed at assessing professional competencies. All other required information overlaps with data that participants are already asked to provide as part of the regular eligibility assessment for the program.
 
Clarify what is done to alleviate the burden
 
To alleviate the burden, data provided by participants for the regular program eligibility assessment (e.g. background information) are directly and secondarily used for research purposes as well. In this way, no duplicate data collection is required, and participation in the study does not add substantially to the effort already needed for program entry
			
12.2 Risk Does the participant run a risk of injuries and/or other discomfort as a result of participating in this study? For example: risk of falling while doing exercises	Yes, minimal risk 	Yes, more than minimal risk 	No 

If yes, please explain what the risk entails. NA Clarify what is done to alleviate the risk. NA		

Appendix 1:

To identify the number of nursing newcomers in the region interested in participating a questionnaire was developed in 2021 and processed using REDCap (Research Electronic Data Capture, Vanderbilt University). In addition to indicating whether someone was interested in participating, information could be provided on professional background, credential evaluation, legal status, years of education and work experience, type of clinical experience, entrustable professional activities, and proficiency in Dutch and English. The questionnaire was published in 16 different languages in addition to Dutch: English, French, Spanish, Persian, Farsi, Polish, Syrian Arabic, Kurdish, Ukrainian, Russian, Uzbek, Turkmen, Dari, Pashto, Bahasa Indonesia, and Turkish. It was disseminated online via a public survey link. In March 2022, the first version of the survey was sent to 22 language schools in the Northern provinces and shared via various social media channels, such as the municipality of Groningen, the Foundation for Refugee Students (UAF) and a national platform that supports connections between refugees and local communities, businesses, and organizations (RefugeeStartForce) with the following text: 'Possible job opportunity for asylum seekers or newcomers in the region of Groningen with a background as scrub nurse at an operating theater OR nurse at the nursing ward/ care unit. Are you interested to be guided to a job as a full team member at the operating theatre or nursing ward? In that case please click on the link below and fill in the form (3 minutes) on your smartphone or tablet:

www.redcap.link/nieuwkomers. Questionnaire in Dutch, English, Français, Español, زبان فارسی, Polski, العربية السورية, Kurdî, українська, русский, O'zbek, Türkmençe, دری, پښتو, Bahasa Indonesia, Türkçe.' The version available through this link is already an updated second version, after it became clear that there were enough potential participants to further shape the program. The questionnaire was updated a third time (December 2023) for scaling up to the other three Northern provinces and then a fourth time for scaling up to four hospitals in the Randstad which can be viewed via www.redcap.link/trajectnieuwkomers.

Appendix 2:

Ontworpen fasttrack integration trajectory: The language centre of the University of Groningen developed a vocational language course as part of this project:

Vocational language course

General Course Outline – Customized Program: The specialized language course for nurses focuses on the essential language skills needed in nursing practice. It is based on the book 'De taal van de verpleging', designed for foreign healthcare professionals at A2 level, with word lists in English, Polish, Lithuanian, and Spanish. The course also incorporates contemporary texts, videos, websites, and other relevant materials. Practical Information: The course consists of 24 lessons, held twice a week, each lasting 2 hours, for a total of 48 contact hours. Additionally, at least 48 hours of self-study are required. The program runs for approximately 3 to 3.5 months.

Once participants reach the minimum Dutch language level (A2), they are required to successfully complete this 3.5 month course. Additionally, the UAF offers separate intercultural communication courses for both participants and their ward nurse mentors ('buddies'):

Intercultural communication training for newcomers and buddies For Newcomers

Goal: Communication is essential in healthcare. Whether engaging in a conversation with a client, discussing matters with family members, or handing over information to colleagues, effective communication plays a key role. In any conversation, it is not only the words spoken that matter—facial expressions and body language (non-verbal communication) are equally important. During the intervision meetings, we address questions and challenges from daily work practice, particularly those related to cultural differences, language, and communication. Additionally, we cover the following topics:

- Perspectives on health, illness, birth, and death across different cultures
- Various levels of cultural differences
- Indirect and direct communication styles
- Differences in time perception
- Understanding personal space
- Developing intercultural sensitivity

The training focuses on Dutch workplace culture and provides insights into communication, cultural awareness, and the skills needed to function effectively. It explores written and unwritten rules, direct and indirect feedback, time management, and workplace behavior and attitudes.

The initial training sessions were organized by the UAF in collaboration with the LC. Currently, the training is provided by Leerzorg in partnership with the LC. In principle, each group participates in five intervention sessions over the first eight months, with each session lasting two hours.

For buddies

A training on workplace skills and culture is also provided to buddies and other interested nurses. This interactive training combines knowledge sharing and information exchange with engaging, hands-on activities. The training is a one-time session lasting four hours and covers the following topics:

- Diversity and inclusion
- Cultural self-awareness and understanding of unwritten rules and dimensions
- Employment of refugee professionals/newcomers in the Netherlands: challenges and opportunities
- Guidance and translating knowledge into practice

Those who attain B1-level Dutch and complete the vocational language course begin working as assistant nurses, salaried as care assistants (a hospital role created specifically for this programme). The programme follows a work-study model with task-differentiated development across three hospital-based phases while participants work as assistant nurse:

- Phase 1 introduces the Dutch healthcare system, culture, and practical language use.
- Phase 2 delivers procedural and professional training by the accredited provider Leerzorg preparing candidates for the nursing competence assessment.
- Phase 3 focuses on developing professional nursing skills in practice.

Procedural and professional training in preparation for the nursing professional competence assessment provided by an accredited training organization Leerzorg

A training program to prepare for the professional competence assessment for internationally educated nurses. This assessment consists of three components: (1) a theoretical knowledge test, (2) a practical exam on nursing skills, and (3) an interview focused on clinical reasoning. The preparatory training includes an online program, theoretical foundations based on the book "Niveau 4 onder de knie", the Vilans protocols for nursing procedures, 8 classroom teaching sessions, and individual coaching. Preparation for components:

- 1 – the knowledge test – includes various elements such as practicing sample questions, completing assignments, attending lessons, becoming familiar with clinical conditions, and gaining understanding of different healthcare sectors, including psychiatry, hospital care, elderly care, home care, and care for individuals with intellectual disabilities.
- 2 – nursing skills – includes, among others, dosage calculations and practice in the skills lab for procedures such as bladder catheterization, injections, feeding tubes, and peripheral IV insertion. As part of component
- 3 – the clinical reasoning interview – participants practice with clinical case studies.

The phases last approximately 4–6, 6–8, and 4–6 months, respectively. Participants are paired with one or two dedicated nurse buddies for onward support and to help set learning objectives. Additional support, such as extra language assistance or coaching by a medical content advisor, is available if needed.

In addition to medical guidance, a key aspect of the programme is the tailored support provided in areas such as municipal contact, registration in the Dutch healthcare system, and, where needed, engagement with other relevant organisations. A project leader with expertise in supporting healthcare newcomers was appointed.

Appendix 3:

The first questionnaire, issued in 17 different languages, requested consent to store the data in the following manner: ‘The personal data that you enter will be processed. Your data will be stored for a maximum period of 1 year. Do you give permission?’

In the updated version in 2023, consent was requested in the following manner in seven different languages (Dutch, Turkish, English, Arabic, Ukrainian, Russian, and Spanish), because previously the questionnaire had only been completed in these languages and not in any of the other 10: ‘The personal data you provide will be processed and stored for a maximum period of 4 years. The other data you provide will be processed and stored for a period of 6 years (anonymized after 4 years). These data will be analyzed to assess how well this program fits your needs and to understand where newcomers may need additional support. Do you give consent for this?’

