3.3 Research questions

What is the proportion of participants who progressed as planned or successfully complete the program at 3, 6, and 10 years after start of the programme? What is the societal business case of the programme and what opportunities for improvement can be identified to optimize its sustainability through a qualitative analysis of the impact on both participants and hospital departments? To what extent do competencies across different domains provide insight into when a participant may require additional support? To what extent do conscious or unconscious racial microaggressions occur in the workplace and what opportunities exist to address and mitigate the unconscious form?

4. Study design

4.1 Mono- or multicenter study.	Monocenter study 	Multicenter study 
--	--	--

4.2 Retrospective study or prospective study		Retrospective study 	Prospective study 
4.3 Cross-sectional or follow-up study		Cross-sectional study 	Follow-up study 
4.4 Quantitative or qualitative study		Quantitative study 	Qualitative study 
4.5 Pilot or explorative study?	Not applicable 	Pilot study 	Explorative study 

Explain why it is a pilot or explorative study.

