7.2.2 If consent is asked complete this section		
7.2.2.1 if the potential participant is a patient:		
First contact with potential participant is made by the treatment provider, either by accompanying letter or in person.	Yes 	No 
Informed consent procedure, including signing the IC, will be carried out by the researcher/ research nurse (not the treatment provider).	Yes 	No 
7.2.2.2 For participants that are either patients or non-patients:		

• Recruitment:
 
Potential participants can register via a custom public survey URL: https://redcap.link/trajectnieuwkomers. This link is shared by organizations such as UAF, COA, and municipalities with their clients. Until now, participants who signed up were asked to provide consent for the processing and storage of their personal data for a maximum of four years. In addition, they could consent to the processing and storage of other data they provided for up to six years (after four years anonymized) for research purposes to analyze how well the trajectory fits the participant and to identify areas where newcomers may need additional support (Appendix 4).
 
With the start of this study, participants who register will:
 
 1 Be asked to provide consent for the processing and storage of personal data for up to four years to determine their eligibility for participation in the trajectory. 2 Receive the attached participant information letter and be asked to digitally sign the consent form, granting permission to use their data for research purposes, the analyses as intended within this study. 
Although the 49 participants already enrolled have previously provided consent for the prospective storage of their data, they will be asked again to provide consent for the use of their data for research purposes. This seems justified by the societal and scientific value of these outcomes as analyzing these data may help optimize the trajectory for future participants in other hospitals and improve the chances of successful integration for nursing newcomers. Only the data of participants who provide this additional consent will be used to determine the
		

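### Section 7.2.2.2 misstates the consent on which the earliest entrants' data were stored, and the primary proportion then counts only those of them who consent again

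*Protocol*

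**What the plan says.** **Past consent.** Section 7.2.2.2 gives one account for everyone who registered before this study: "participants who signed up were asked to provide consent for the processing and storage of their personal data for a maximum of four years". It adds that other data could be kept for up to six years for research, anonymised after four. Appendix 3 gives two accounts. The first questionnaire read "Your data will be stored for a maximum period of 1 year". The version updated in 2023 read "The personal data you provide will be processed and stored for a maximum period of 4 years", with six years for other data and anonymisation after four. Section 3.1 refers to Appendix 3 for the consent under which programme data were stored.

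**Consent from study start.** New registrants are asked for "processing and storage of personal data for up to four years to determine their eligibility for participation in the trajectory". Separately, they receive an information letter and sign a research consent for this study's analyses. The 49 already enrolled are asked again for research consent. Only those who give it count towards the primary outcome, and the number who do not is recorded.

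**Follow-up and identifiers.** Section 3.3 asks for the primary proportion "at 3, 6, and 10 years after start of the programme". Under section 9.2, "direct identifiers are temporarily accessible to the study coordinator to complete essential outcome data", and identifiers are replaced by a code once all required data are in. Section 9.1 archives data for 15 years after the study ends.

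**The concern.** The two descriptions of past consent cannot both be right for people who registered on the first questionnaire. They are the earliest entrants, with the longest follow-up. Their one-year permission is shorter than the trajectory itself, and the protocol gives no basis for holding their data between the end of that year and the new request.

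The statistical consequence comes through the renewed consent. The primary proportion is restricted to those of the 49 who agree. People who left early or did poorly may be harder to reach or less willing to sign, and people doing well may be easier to find because they still work in the hospital. Either would move the proportion, and a reader shown only the consenters' estimate could not judge by how much. The early entrants weigh most at the 3-year look.

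**Working it through.** **1. Enrolment projection (section 6.3).** North: 3.3 × 5 hospitals × 6 years = 99 (stated 98). Randstad: 3.3 × 4 × 6 = 79.2 (stated 80). Maximum: 49 + 98 + 80 = 227, as stated. Lower end: 0.7 × 227 = 158.9, the stated 159. So the 49 are 49/227 = 21.6% to 49/159 = 30.8% of the projected total.

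**2. One year against one trajectory (Appendix 2).** A language course of 3.5 months plus phases of 4–6, 6–8 and 4–6 months gives 3.5 + 14 = 17.5 to 3.5 + 20 = 23.5 months. A one-year term ends before a planned trajectory does.

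**3. When one-year permissions ended.** The survey was first sent in March 2022, and a new version followed in December 2023 (Appendix 1). Assume that the term runs from registration and that the one-year text was not used after December 2023. The permissions then ended between March 2023 and December 2024. The protocol's reference list has access dates in May 2025, so the renewed request comes later than all of these.

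**4. Past terms against the looks, counted from each person's registration.**

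| Past term | Year 3 | Year 6 | Year 10 |
|---|---|---|---|
| 1 year | no | no | no |
| 4 years, personal data | yes | no | no |
| 6 years, other data | yes | stored, but anonymised from year 4, so a new outcome cannot be linked | no |

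If the looks are calendar dates counted from March 2022 (an assumption), the ten-year look falls in March 2032. Someone registered by March 2025 could be linked until March 2029 at the latest, and their other data kept until March 2031. The ten-year look is out of reach on either reading.

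**5. Effect on the primary proportion.** Let k enrolled people have unknown outcome, and let s of n consenters succeed. The bounds over all enrolled are s/(n + k) and (s + k)/(n + k), so the range is k/(n + k) wide. The documents give no k, so these values are illustrations only.

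- 3-year look, if the cohort is then the 49: k = 10 gives 10/49 = 20.4 points and k = 25 gives 25/49 = 51.0 points. For example, 31 successes among 39 consenters is 79.5%, with bounds 31/49 = 63.3% and 41/49 = 83.7%.
- Full cohort: k = 10 gives 10/227 = 4.4 to 10/159 = 6.3 points; k = 25 gives 25/227 = 11.0 to 25/159 = 15.7 points.

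**6. The same seen as bias.** Assume a true proportion of 0.80 and k early entrants missing, either all failures or all successes.

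| Total | k | Consenters-only estimate |
|---|---|---|
| 227 | 10 | 171.6/217 = 0.791 to 181.6/217 = 0.837 |
| 227 | 25 | 156.6/202 = 0.775 to 181.6/202 = 0.899 |
| 159 | 10 | 117.2/149 = 0.787 to 127.2/149 = 0.854 |
| 159 | 25 | 102.2/134 = 0.763 to 127.2/134 = 0.949 |

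These are extremes, not forecasts.

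**The case against.** The strongest answer is that a lapsed term does not mean lost data. All 49 are asked for new research consent, so early entrants leave the analysis only by refusing or not being reached. Nothing says they cannot be reached, and the number who do not consent is recorded. This stands, and it limits the point to non-response to the renewed request.

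A reader might infer that for new registrants, too, follow-up ends four years after registration and no outcome can be linked afterwards. The documents do not support this. The four-year permission serves eligibility assessment, and a separate research consent covers the analyses. That form is not among the pages at hand, so its term cannot be called missing. Section 9.2 ties the removal of identifiers to completion of data collection, not to a date.

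A reader might also put a number on the loss. Even enrolment from March 2022 to March 2025, with the text changing in December 2023, gives 21/36 × 49 ≈ 29 people on the one-year text. But even enrolment is assumed, and Appendix 1 describes a second version before December 2023 whose consent text is not given. Treating all of them as lost would further require that none consents again.

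It is fair to add that people still in training at three years and on schedule count as successes by definition, so their presence is no defect. Section 6.5 also foresees sensitivity analyses for missing data, and their detail may be left to an analysis plan. What remains is that the protocol itself fixes a consenters-only primary proportion, and its account of past consent conflicts with its own appendix.

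**Conclusion.** The inconsistency is real: section 7.2.2.2 reports four years for all past registrants, and Appendix 3 reports one year for the first questionnaire. Those on the one-year text were past their term before the renewed request, on the two assumptions in step 3. No past term supports linked outcomes at ten years.

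The effect on the primary result is possible but not demonstrated. It runs through refusal or non-contact among the 49, and its size depends on how many that is. Per person of unknown outcome, the best/worst-case range widens by 1/49 = 2.0 points if the 3-year look rests on the 49 (calendar reading, programme start about March 2022), and by 1/227 = 0.4 to 1/159 = 0.6 points in the full cohort. How many of the 49 signed the one-year text lies somewhere from 0 to 49 and cannot be narrowed from the documents. The point is minor.

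**What to change.** 1. In section 7.2.2.2, describe both past consent texts as Appendix 3 has them (one year; four years for personal data and six for other data, anonymised after four), and state how many of the 49 fall under each.
2. Before the renewed consent forms go out, check that the research consent's term for linkable data reaches the last planned look, and make section 7.2.2.2 agree with it.
3. Report the primary proportion with all enrolled participants in the denominator. Count those who refuse or cannot be reached as outcome unknown, and give best/worst-case bounds beside the consenters-only estimate. This uses only a count of such people, which the protocol largely plans to record already; say explicitly that the count includes those not reached.

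The cost is some wording, one count by questionnaire version, and a 3-year result that may look less precise. If the term proves too short after the forms have been sent, a further consent round would be needed.
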